4.2 Study Population

All patients with symptomatic gall stones who will be treated by laparoscopic cholecystectomy

4.3 Study Area

Surgical ward of No.(1) Military Hospital (700 bedded), Pyin Oo Lwin

4.4 Study Period

This study will be carried out from December 2019 to December 2021.

4.5 Sample size determination

Target population of this study is patients with symptomatic gall stones requiring laparoscopic cholecystectomy and it will be carried out in surgical wards of No. (1) Military Hospital (700 bedded). The minimal required sample size can be calculated as follow;

$$n = \frac{(Z_{1-\alpha/2} + Z_{1-\beta})^2 (\sigma_1^2 + \sigma_2^2)}{(\mu_1 - \mu_2)^2} \quad (\text{Lwanga S.K. \& Lemeshow S., 1993})$$

n= minimum required sample size

For 95% confidence level, $Z_{1-\alpha/2} = 1.96$ (for two sided)

For power 80%, $Z_{1-\beta} = 0.84$

$\mu_1 = 2.85$ (Analgesic need after CLC) (Sreenivas et al, 2016)

$\mu_2 = 2.31$ (Analgesic need after TPPOP LC) (Sreenivas et al, 2016)

$\sigma_1 = 0.79$

$\sigma_2 = 1.02$

n = 44

After adding 10% drop out

$n_1 = 49$

The minimum required sample size will be 49 in each group, 98 in total.

By receiving the hospital statistics, patients who was treated by laparoscopic cholecystectomy were about 150 patients a year in No.(1) Military Hospital (700 bedded) Pyin Oo Lwin. So the require sample size can be met within the study period.

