3.2 Objectives

1. To compare the operation time between conventional laparoscopic cholecystectomy (CLC) and two ports plus one puncture laparoscopic cholecystectomy (TPPOP LC)
2. To compare the intraoperative complications of both study groups.
3. To compare the conversion rate of both study groups.
4. To compare the postoperative complications, postoperative pain, postoperative hospital stay of both study groups.

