4.8.10 Postoperative outcomes

Postoperative outcomes include postoperative pain, postoperative complications and postoperative hospital stay.

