4.10 Data analysis

Data will be recorded by using a pre-structured proforma. Data will be collected as categorical as well as numerical variables. Record files will be constructed in Microsoft Excel. The base line data will be entered into data base file. The final data file in Microsoft Excel will be exported as data base file. The categorical data will be calculated by appropriate statistical method such as Chi-square. For continuous variables, the statistical significance of patients will be analyzed by two independent Student's t test. The level of significance will be set at $P < 0.05$. After data analysis, the result will be presented in dummy tables and figures.

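### The trial is sized only on analgesic need, which no objective names; no outcome is primary, and one P < 0.05 level covers ten two-arm tables

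*Protocol*

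**What the plan says.** **Sizing.** Protocol section 4.5 uses one outcome. The control mean is 2.85, labelled "Analgesic need after CLC"; the corresponding mean for the two-port arm is 2.31; the SDs are 0.79 and 1.02. With two-sided 5% significance and 80% power this gives 44 per group, raised to 49 for 10% dropout, 98 in total. No unit is given for the means.

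**Objectives.** Section 3.2 lists operation time, intraoperative complications and conversion rate, and then: "To compare the postoperative complications, postoperative pain, postoperative hospital stay of both study groups". Analgesic need is not among them. Section 4.8.10 leaves it out as well: "Postoperative outcomes include postoperative pain, postoperative complications and postoperative hospital stay".

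**Where analgesic need does appear.** Rescue tramadol is recorded (4.7.8, 4.7.9 and proforma part G), defined (4.8.12), listed as a variable in milligrams (4.9), and compared between arms as doses in Table 12, with a total, a mean ± SD and a P value.

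**Testing.** Section 4.10 says "The level of significance will be set at" P < 0.05. It singles out no outcome, and no section calls any outcome primary.

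**The concern.** A power statement is useful when it belongs to the question the trial will answer. Here the 80% belongs to an outcome outside the stated objectives, and the objectives themselves carry no stated power. With no primary outcome and one threshold for everything, any P value below 0.05 among the planned comparisons could become the headline result. The study is open label (4.1), so leaving that choice until the data are in is a real weakness: the nominal 5% error rate would not describe the trial's conclusion.

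**Working it through.** **1. Reproduce the sample size.** Inputs from section 4.5: difference 2.85 − 2.31 = 0.54; sum of variances 0.79² + 1.02² = 0.6241 + 1.0404 = 1.6645; (1.96 + 0.84)² = 7.84.

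n = 7.84 × 1.6645 / 0.54² = 13.0497 / 0.2916 = 44.75 per group.

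The plan's 44 is this figure rounded down; rounded up it is 45. Dropout: 44 / 0.9 = 48.9, so 49, as stated; 45 / 0.9 = 50. The arithmetic is not the fault.

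**2. Power if analgesic need is the single primary outcome.** Normal approximation, power = Φ(0.54 / √(1.6645/n) − 1.96):

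- n = 44: Φ(2.776 − 1.96) = 79.3%
- n = 45: Φ(2.808 − 1.96) = 80.2%
- n = 49: Φ(2.930 − 1.96) = 83.4%

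**3. Count the comparisons.** Dummy Tables 3, 4 and 7 to 14 each show both arms with a P value column, which makes ten at one test per table. Table 5 also has a P value column but shows only group A; Table 6 has none.

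**4. Chance of at least one P < 0.05 when no true difference exists.**

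| Assumption for ten tests at 5% | Chance |
|---|---|
| Independent: 1 − 0.95¹⁰ | 40.1% |
| Common correlation 0.3 (simulated) | about 35% |
| Common correlation 0.5 (simulated) | about 29% |
| Common correlation 0.7 (simulated) | about 21% |

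The correlations are assumptions; the protocol gives none. All rows take each test to reject at a full 5%.

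**5. Do the rare-event tables reject at 5%?** Section 1.3 puts conversion to open surgery below 1% for the conventional arm and at about 0.18% for the two-port arm. At 49 per arm that is under 49 × 0.01 = 0.49 and about 49 × 0.0018 = 0.09 expected events. An uncorrected chi-square test needs 4 against 0 to reach significance:

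- 4 v 0: χ² = 98 × (4 × 49)² / (49 × 49 × 4 × 94) = 4.17, P = 0.041
- 3 v 0: χ² = 98 × (3 × 49)² / (49 × 49 × 3 × 95) = 3.09, P = 0.079

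On those rates Table 7 can hardly ever reject, so it adds almost nothing to the false-positive chance. Summing binomial probabilities with 49 per arm and the same true rate in both, the test rejects 0.2% of the time at 1%. Section 1.2 quotes a higher conversion range of 2% to 5% for laparoscopic cholecystectomy generally; at those rates the figures are 1.3% and 5.3%, so the discount depends on which rate applies.

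**6. Cost of keeping all ten confirmatory.** With Bonferroni at 0.05 / 10 = 0.005 each, analgesic need alone would require 76 per group (85 with dropout, 170 in total). At 44 to 49 evaluable per group, its power would be 48.8% to 54.9%.

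**7. Unit of the sized outcome.** Section 4.7.9 gives tramadol at 1 mg/kg. At 50 kg, the body weight where that section changes the paracetamol amount, one administration is 50 mg. Means of 2.85 and 2.31 with SDs near 1 cannot describe milligrams on that scale. They look like counts, but this is an inference. Section 4.9 says milligrams and Table 12 says doses.

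**The case against.** **The sized outcome is analysed and is close to objective 4.** Rescue tramadol is given for pain, triggered by a VAS score or a complaint of pain, and has its own comparison in Table 12. This stands: a reader might infer that the trial is powered for something it never analyses, and the documents do not support that. But section 4.8.11 defines postoperative pain as somatic pain at the port site, measured by VAS, and 4.8.12 defines rescue analgesia separately. Naming pain in an objective does not name analgesic need.

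**Multiplicity may be handled in a statistical analysis plan that is not shown.** This is fair for the adjustment method. It does not cover the mismatch, because the sizing outcome, the objectives and the single significance level are all fixed in the protocol and do not line up.

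**The error inflation is easily overstated.** This also stands. The 40% needs ten independent tests that each reject at 5%. Tables 8 to 11 are the same patients' VAS at four times, a VAS above 4 triggers the drug counted in Table 12, and rare events seldom reject. A reader might go further and count the rows of Tables 4, 12 and 13 separately, reaching about 20 tests and 64%. The protocol does not say that each row is tested, so that figure should not be used. Nor does section 4.10 declare each table significant in its own right; it gives one general level and no order of importance.

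**Conclusion.** The concern holds in this form: the stated 80% power is attached to an outcome that no objective names, no outcome is primary, and one threshold serves ten two-arm tables. The family-wise error is well above 5%, but the documents do not fix its value. Forty per cent is the figure for independent tests; 21% to 35% follows from assumed correlations of 0.7 to 0.3; sparse tables pull it lower still. The sample size arithmetic is sound apart from rounding 44.75 down. The claim that the power carries over to a named primary outcome rests on one unconfirmed assumption: that 2.85 and 2.31 are numbers of rescue doses.

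**What to change.** - In sections 3.2, 4.8.10 and 4.10, name one primary outcome: the total number of rescue tramadol doses per patient over 0-48 h (the Table 12 total), tested once at two-sided 0.05, with no separate P value for each 12-hour period.
- State that unit consistently in 4.5, 4.9 and Table 12. Check against the cited source that 2.85 and 2.31 are in it, and restate the power if they are not.
- Label every other outcome secondary, report it as an estimate with a 95% confidence interval and no stand-alone claim of significance, and adjust the dummy tables to match.

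Resizing on an outcome already among the objectives would also remove the mismatch, but needs new planning figures. Neither route by itself tests the section 3.3 hypothesis that the two techniques are equally safe and effective; the primary outcome should not be presented as doing so.

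**Cost.** Text changes in the sections above and in the section 5 tables. No new data are needed, since proforma part G already records the time and amount of each rescue dose. Sample size moves from 44 to 45 per group before dropout (49 to 50 after). The downside is that secondary results can no longer be claimed as significant on their own.

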4.6.2 Exclusion Criteria

4.6.2.1 Patients with ASA III, IV & V

4.6.2.2 Previous upper abdominal surgery

4.6.2.3 Patients with common bile duct pathology

4.6.2.4 Patients with clinical or USG suspected gall bladder cancer

4.6.2.5 Patients with bleeding disorders

4.6.3 Randomization procedure

Randomization will be done by block design in this study. The patients will be enrolled into the study according to inclusion and exclusion criteria. Then they will be randomized by block randomization method. For sample size of 98 in total, there will be 10 blocks, each having 10 patients. In each block with 10 cases, two methods will be allocated in random order. Random block design will be generated by using Graphpad Prism Software. The first case will be allocated into one block by envelope method. Then following 9 cases will go into the same block in order. After completing one block, the same procedure will be done for another block for 10 patients. The blocks used for this randomization is shown below.

1 2 3 4 5 6 7 8 9 10

Block1	A	A	B	B	B	A	A	B	A	B
--------	---	---	---	---	---	---	---	---	---	---

Block2	A	B	B	A	B	B	A	B	A	A
--------	---	---	---	---	---	---	---	---	---	---

Block3	A	A	B	B	A	B	B	A	A	B
--------	---	---	---	---	---	---	---	---	---	---

Block4	B	A	A	B	B	A	A	B	B	A
--------	---	---	---	---	---	---	---	---	---	---

Block5	B	A	B	A	A	A	B	B	A	B
--------	---	---	---	---	---	---	---	---	---	---

Block6	B	B	A	B	B	A	A	A	B	A
--------	---	---	---	---	---	---	---	---	---	---

Block7	A	A	B	A	A	B	A	B	B	B
--------	---	---	---	---	---	---	---	---	---	---

Block8	A	B	A	B	B	B	A	B	A	A
--------	---	---	---	---	---	---	---	---	---	---

Block9	B	A	B	A	A	B	B	A	A	B
--------	---	---	---	---	---	---	---	---	---	---

Block10	B	B	A	A	B	A	B	A	B	A
---------	---	---	---	---	---	---	---	---	---	---

Method A : Conventional laparoscopic cholecystectomy (CLC)

Method B : Two ports plus one puncture laparoscopic cholecystectomy (TPPOP LC)

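### Section 4.5 truncates 44.75 to 44 per group; rounded up and inflated for 10% drop-out, the minimum is 50 per group and 100 in total, not 49 and 98 (minor)

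*Protocol*

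**What the plan says.** Protocol section 4.5 prints a formula for comparing two means, with these inputs: two-sided 95% confidence (z = 1.96), 80% power (z = 0.84), mean analgesic need 2.85 after conventional cholecystectomy and 2.31 after the two-port technique, and standard deviations 0.79 and 1.02. It defines n as the minimum required size and gives n = 44. The next step is introduced by "After adding 10% drop out" and leads to 49. The section then concludes: "The minimum required sample size will be 49 in each group, 98 in total".

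Section 4.6.3 carries the total forward: "For sample size of 98 in total, there will be 10 blocks, each having 10 patients". It prints ten blocks, each with five A and five B, which makes 100 places. Section 4.10 names the two-sample Student's t test for continuous variables, at a significance level of 0.05.

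**The concern.** A result described as a minimum should satisfy the formula that produced it. The printed 44 looks too low for the printed inputs, and the slip carries through the drop-out step into both the per-group and the total figure. At stake is whether a reader can reproduce the sample size from the protocol, and whether the stated 80% power is still met once the planned losses have occurred.

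**Working it through.** **Inputs** (all from section 4.5): z values 1.96 and 0.84; means 2.85 and 2.31, difference 0.54; standard deviations 0.79 and 1.02; drop-out 10%.

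**1. The protocol's formula**

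n = (1.96 + 0.84)² × (0.79² + 1.02²) / 0.54²

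- (1.96 + 0.84)² = 7.84
- 0.79² + 1.02² = 0.6241 + 1.0404 = 1.6645
- 0.54² = 0.2916
- n = 7.84 × 1.6645 / 0.2916 = 44.75

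With unrounded z values the result is 44.80. Rounding up and rounding to the nearest integer both give 45. Only dropping the decimals gives the printed 44.

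**2. The protocol's drop-out step**

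The section does not show how it inflated the figure. Both common ways lead from 44 to the printed 49:

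- 44 / 0.9 = 48.9, rounded up to 49
- 44 × 1.1 = 48.4, rounded up to 49

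So 49 and 98 follow from 44, and on either route a fraction was rounded up at this step although the one before it was rounded down.

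**3. The same step from 45**

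- 45 / 0.9 = 50
- 45 × 1.1 = 49.5, rounded up to 50

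Either way the result is 50 per group, 100 in total. Carrying 44.75 forward unrounded also ends at 50 (44.75 / 0.9 = 49.7; 44.75 × 1.1 = 49.2).

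**4. Power**

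Normal approximation: power = Φ(0.54 / √(1.6645/n) − 1.96). At n = 44 this is Φ(2.776 − 1.96) = 79.3%. The t-test column uses the noncentral t distribution with common standard deviation √(1.6645/2) = 0.912 and 2n − 2 degrees of freedom.

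| Evaluable per group | Normal formula | t test |
|---|---|---|
| 44 | 79.3% | 78.4% |
| 45 | 80.2% | 79.3% |
| 46 | 81.0% | 80.2% |
| 49 | 83.4% | 82.7% |
| 50 | 84.1% | 83.4% |

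If 98 are randomised and 10% are lost, 98 × 0.9 / 2 = 44.1 per group remain, and power on the normal formula is 79.4%. If all 100 places are filled and 10% are lost, 45 per group remain, and it is 80.2%.

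**The case against.** The strongest case on the other side is that this makes no practical difference. The gap is one patient per group and about 0.7 percentage points of power on the formula used. It arises only if the whole 10% is lost: with no losses, 49 per group gives 83.4%. The means and standard deviations are point estimates from one cited study, and their uncertainty far exceeds a quarter of a patient. All of this stands and is why the point is minor. It does not make 44 the right answer to the printed formula.

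A second objection is that the t-test figure cuts against the remedy, since 45 per group gives only 79.3% by that test and 46 would be needed to pass 80%. That is correct. The protocol sized the trial with the normal formula, and the correction applies that formula as written. The t-test figures should be reported beside it, not used as the pass mark for one number and ignored for the other.

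A reader might infer two stronger things, which the protocol does not support:

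- *That sections 4.5 and 4.6.3 contradict each other, 98 against 100.* Both name 98. Section 4.5 calls it a minimum, and ten is the smallest number of whole blocks of ten that covers it. A list slightly longer than the minimum is normal with blocked allocation.
- *That an arm may fall short of 49.* This needs enrolment to stop at exactly 98, which the protocol nowhere says, and the last block drawn to be 2, 7 or 8, whose final two places belong to the same arm. The split would then be 48/50 or 50/48. After 10% loss, power would be 79.2% to 79.6%, practically the same as for 49/49.

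What remains of the second is only that section 4.6.3 could say outright that the last block is filled.

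**Conclusion.** Minor, but wrong as written. With the protocol's own formula and inputs, the minimum is 45 evaluable per group, hence 50 per group and 100 in total after the 10% allowance. The printed 49 and 98 are short by one per group and two overall. At the full assumed loss from 98, power is about 79% on the normal formula, or 78.4% on the t test, against the stated 80%.

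This takes the section 4.5 means, standard deviations, two-sided 5% level and drop-out rate at face value. It does not show that the trial will be underpowered: with fewer losses, or with all ten printed blocks filled, power on the protocol's formula is above 80% or very close to it. No planned test or estimate changes.

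**What to change.** In section 4.5, show the formula result as 44.75, rounded up to 45 evaluable per group, then 45/0.9 = 50 per group and 100 in total. In section 4.6.3, replace 98 by 100, so that the target equals the ten printed blocks of ten and it is clear that the last block is filled. Add that 45 per group gives 80.2% power on the normal formula and 79.3% on the t test.

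If the sponsor prefers to keep 98, state the power at 44 evaluable per group as about 79% (normal approximation) in place of 80%.

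The cost is wording plus two patients. The allocation list already has the places, and section 4.5 reports about 150 laparoscopic cholecystectomies a year at the hospital.

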4.6 Sampling method and procedure

The patients will be selected according to the following criteria:

4.6.1 Inclusion Criteria

All patients with symptomatic gall stones who will be treated by laparoscopic cholecystectomy.

4.6.2 Exclusion Criteria

4.6.2.1 Patients with ASA III, IV & V

4.6.2.2 Previous upper abdominal surgery

4.6.2.3 Patients with common bile duct pathology

4.6.2.4 Patients with clinical or USG suspected gall bladder cancer

4.6.2.5 Patients with bleeding disorders

4.6.3 Randomization procedure

Randomization will be done by block design in this study. The patients will be enrolled into the study according to inclusion and exclusion criteria. Then they will be randomized by block randomization method. For sample size of 98 in total, there will be 10 blocks, each having 10 patients. In each block with 10 cases, two methods will be allocated in random order. Random block design will be generated by using Graphpad Prism Software. The first case will be allocated into one block by envelope method. Then following 9 cases will go into the same block in order. After completing one block, the same procedure will be done for another block for 10 patients. The blocks used for this randomization is shown below.

1 2 3 4 5 6 7 8 9 10

Block1	A	A	B	B	B	A	A	B	A	B
--------	---	---	---	---	---	---	---	---	---	---

Block2	A	B	B	A	B	B	A	B	A	A
--------	---	---	---	---	---	---	---	---	---	---

Block3	A	A	B	B	A	B	B	A	A	B
--------	---	---	---	---	---	---	---	---	---	---

Block4	B	A	A	B	B	A	A	B	B	A
--------	---	---	---	---	---	---	---	---	---	---

Block5	B	A	B	A	A	A	B	B	A	B
--------	---	---	---	---	---	---	---	---	---	---

Block6	B	B	A	B	B	A	A	A	B	A
--------	---	---	---	---	---	---	---	---	---	---

Block7	A	A	B	A	A	B	A	B	B	B
--------	---	---	---	---	---	---	---	---	---	---

Block8	A	B	A	B	B	B	A	B	A	A
--------	---	---	---	---	---	---	---	---	---	---

Block9	B	A	B	A	A	B	B	A	A	B
--------	---	---	---	---	---	---	---	---	---	---

Block10	B	B	A	A	B	A	B	A	B	A
---------	---	---	---	---	---	---	---	---	---	---

Method A : Conventional laparoscopic cholecystectomy (CLC)

Method B : Two ports plus one puncture laparoscopic cholecystectomy (TPPOP LC)

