4. RESEARCH METHODOLOGY

4.1 Study Design

Hospital based open labeled randomized control study

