4.7 Research procedure

4.7.1 Patient selection and data collection

The study population will include those patients with symptomatic gall stones who will be treated by laparoscopic cholecystectomy in No.(1) Military Hospital (700 bedded) and will not be met the exclusion criteria. Complete history will be taken including patient's identification, presenting symptoms, past medical and past surgical history. Thorough physical examination including general and abdominal examination will be performed. Investigations including liver function test, complete blood picture, urea, creatinine, viral serology for preoperative assessment will be done. Abdominal sonography will be carried out. The results will be recorded in the proforma.

After selection of the patients by inclusion and exclusion criteria, eligible patients will be counseled by the author about nature of disease, type of operation to be performed and possible complications. If the patient agrees to participate, a written informed consent will be obtained. The participants will be randomly allocated by block randomization method. Method A conventional laparoscopic cholecystectomy (CLC) will be done for control group and Method B two ports plus one puncture laparoscopic cholecystectomy (TPPOP LC) will be done for study group.

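### One envelope draw settles a whole block of ten, and all ten block sequences are printed in the protocol, so about 90 of the 98 planned allocations can be known before the patient is enrolled in this open-label trial

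*Protocol*

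**What the plan says.** Protocol section 4.6.3 sets out blocked randomization: "For sample size of 98 in total, there will be 10 blocks, each having 10 patients". The envelope is drawn once per block, and no further draw is made for the rest of that block: "The first case will be allocated into one block by envelope method. Then following 9 cases will go into the same block in order". The cycle then repeats: "After completing one block, the same procedure will be done for another block for 10 patients".

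The section introduces the ten sequences with the words "The blocks used for this randomization is shown below", prints each in full, and states below them that A is CLC and B is TPPOP LC. It says the block design comes from randomization software.

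Two other places bear on this. Section 4.1 describes the trial as "Hospital based open labeled randomized control study", so past allocations are visible. Section 4.7.1 says that "eligible patients will be counseled by the author about nature of disease, type of operation to be performed", with written consent and then allocation following. The protocol does not say who draws the envelope, who holds the list or who sees the block number, and it describes no concealment for the second to tenth patients of a block.

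**The concern.** Concealment means that whoever judges eligibility and seeks consent cannot foresee the next assignment. Here one draw settles ten assignments, and the key to those ten is printed in a document that its author, who also counsels patients, necessarily has. Placing consent before allocation does not help if the arm can be read off before the patient is approached.

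There is room for such knowledge to matter. The entry criteria (sections 4.6.1 and 4.6.2) do not exclude inflamed gallbladders or obesity, so technically difficult cases are eligible. Sections 4.7.6 and 4.7.7 make adhesions and inflammation triggers for conversion. If such patients were approached, deferred or ordered with the next arm in view, conversion would be affected directly, and operation time, complications, rescue analgesia and stay plausibly so. These are the outcomes that the trial compares.

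**Working it through.** **Inputs.** From section 4.6.3: ten printed sequences of ten, one draw per block. From section 4.5: 98 patients, 49 per arm, sizing difference 2.85 − 2.31 = 0.54. Transcribed, the ten sequences are all different, each has five A and five B, and five start with each letter.

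**Reading assumed.** Blocks are drawn without replacement, because the text moves on to another block after each one. The protocol does not state this as a rule, so the alternative is also shown.

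**1. Drawn block seen.**
- Positions 2 to 10 of each block are fixed: 10 × 9 = 90 of 100 slots. For 98 patients, the last block has only eight: 9 × 9 + 7 = 88.
- The first patient of a block is also certain when all remaining blocks start with the same letter, as always happens for the last block. With five blocks of each kind in random order, the expected number of such blocks is 1 + 4/6 = 1.67.
- Total: 90 + 1.67 = 91.7 of 100, or 88 + 1.67 = 89.7 of 98. Simulated draw orders agree.
- If blocks could be redrawn: 90 of 100, or 88 of 98.

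**2. Block number hidden, printed list in hand, past allocations visible.**
- Taken against all ten sequences, a block is identified after three to six patients. Blocks 1 to 10 have 6, 7, 6, 7, 6, 7, 7, 7, 6 and 7 certain positions, 66 in total. This is the expected count per 100 if blocks can be redrawn.
- Without replacement, fewer candidates remain as the trial proceeds. Simulation gives 77.3 certain of 100 (75.3 of 98).
- Guessing the likelier arm each time is right for 90.4 of 100 without replacement, and for 85 of 100 if blocks can be redrawn.

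**3. Comparator: concealed list, fixed block of ten, still open label.**
- Over all 252 balanced sequences of length ten, an assignment is certain only once one arm has used its five places. That is 1 + 4/6 = 1.67 per block, or about 17 per 100.
- Guessing the arm with fewer patients so far is right 6.53 times in 10, about 65%.

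| Situation | Certain in advance, per 100 | Best guesses correct |
|---|---|---|
| Block seen | 91.7 | – |
| Block hidden, list printed | 77.3 | 90% |
| Block hidden, list printed, blocks redrawn | 66 | 85% |
| Concealed list, fixed block of ten | 17 | 65% |

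**4. What steering could do (illustration; all inputs below are assumptions except 49 and 0.54).** Suppose ten patients each need 2 extra rescue doses and are split k to 10 − k between CLC and TPPOP LC instead of 5 to 5. Treat the analgesic means in section 4.5 as numbers of doses, since no unit is given there. The shift in the difference is (2k − 10) × 2/49:
- 7/3: 4 × 2/49 = 0.16, or 30% of 0.54
- 8/2: 6 × 2/49 = 0.24, or 45%
- 10/0: 10 × 2/49 = 0.41, or 76%

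With 1 extra dose each, a 10/0 split gives 10 × 1/49 = 0.20, or 38%.

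**The case against.** The strongest reply is that knowable is not the same as known. The protocol does not say that the recruiter sees the drawn block, and it takes all eligible patients, which limits discretionary exclusion. It describes no deferral of surgery dates. A reader might infer that the author does know each next assignment, or that patients will be steered. The documents support neither. This part of the reply stands, and the point is limited to what the procedure makes possible. It does not rescue the procedure, because even a hidden block number leaves about 75 of 98 allocations certain.

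Second, open-label blocking always leaks something. A reader might set the 90% correct guesses against 50%, but that is the wrong benchmark: concealed blocks of ten give about 65%, and blocks of 4 and 6 give about 71% and 68%. The excess due to the printed list is thus about 25 percentage points of guessing accuracy (90 − 65) and about 60 certain allocations per 100 (77 − 17), and more if the block is seen.

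Third, a reader might conclude that no analysis could help. That is too absolute: age and BMI are recorded (section 4.9), and adjusting for them would remove part of the bias. It would not remove selection on features that are not recorded, such as the expected severity of inflammation.

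Fourth, the 10/0 split is extreme, since 2 extra doses are roughly 2 to 2.5 of the standard deviations in section 4.5 (2/1.02 = 2.0; 2/0.79 = 2.5). That is why milder cases are shown beside it.

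The printed table cannot be passed off as an example, because the text calls it the blocks used. A separate analysis plan would not cure the fault either, since the protocol itself fixes how patients are allocated.

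**Conclusion.** The concern holds, and the allocation procedure should be changed before recruitment. Followed exactly, section 4.6.3 lets anyone with the protocol who sees the drawn block know about 90 of 98 allocations in advance. This rests on reading the blocks as used once each; if they could be redrawn, the count is 88 of 98. With the block number hidden, the figures are about 75 of 98, or about 66 of 100 slots if blocks could be redrawn.

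The sequences themselves are balanced and were to be generated at random, so the fault is disclosure and block-level drawing, not the randomness of the list. No concealment is described for the second to tenth patients of a block. How much bias would follow cannot be derived from the documents; under the stated assumptions, moderate to extreme steering would shift the analgesic comparison by 0.16 to 0.41 doses against a sizing difference of 0.54.

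**What to change.** Discard the ten printed sequences and remove them from the protocol. Have a colleague who neither recruits nor operates generate a new list and hold it out of the recruiters' sight. Replace the block-level draw with one sequentially numbered, opaque, sealed envelope per patient, opened only after eligibility is confirmed and consent is signed. State in section 4.6.3 who generates the list, who holds it and who opens the envelopes.

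Block sizes that are not disclosed in the protocol are preferable, but particular sizes are a matter of taste. Most of the gain comes from concealing the list and drawing per patient.

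The cost is one paragraph of amendment, about 100 envelopes and a small task for one existing colleague, a role that the protocol does not yet name. No extra patients are needed.
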